Appendix 4 CDAI Scoring

Clinical Disease Activity Index (CDAI)

Joint	Le	eft	Ri	ght
	Tender	Swollen	Tender	Swollen
Shoulder				
Elbow				
Wrist				
MCP 1				
MCP 2				
MCP 3				
MCP 4				
MCP 5				
PIP 1				
PIP 2				
PIP 3				
PIP 4				
PIP 5				
Knee				
Total	Tender:		Swollen:	

Patie	Patient Global Assessment of Disease Activity																					
Considering all the ways your arthritis affects you, rate how well you are doing on the following scale:																						
																						Very
Well	0	0.5	1.0	1.5	2.0	2.5	3.0	3.5	4.0	4.5	5.0	5.5	6.0	6.5	7.0	7.5	8.0	8.5	9.0	9.5	10	Poor
Your	Your Name Date of Birth Today's Date																					

How to Score the CDAI

Variable	Range	Value
Tender joint score	(0-28)	
Swollen joint score	(0-28)	
Patient global score	(0-10)	
Provider global score	(0-10)	
Add the above values to	(0-76)	
calculate the CDAI score	` '	

CDAI Score Interpretation							
0.0 - 2.8	Remission						
2.9 - 10.0	Low Activity						
10.1 - 22.0	Moderate Activity						
22.1 - 76.0	High Activity						

Appendix 5 ACR Response Criteria

ACR Response Criteria

The ACR (American College of Rheumatology) Criteria is a standard criteria to measure the effectiveness of various arthritis medications or treatments in clinical trials for Rheumatoid Arthritis. The ACR is used to maximally discrimate effective treatment for placebo treatment in clinical trials. The ACR criteria is indicated as ACR 20, ACR 50, or ACR 70. The ACR is reported as % improvement, comparing disease activity at two discrete time points (usually baseline and post-baseline comparison).

- ACR20 is ≥ 20% improvement
- ACR50 is ≥ 50% improvement
 - ACR50 reponders include ACR20 responders
- ACR70 is \geq 70% improvement
 - o ACR70 reponders include ACR20 & ACR50 responders

Definition

The ACR Criteria is a dichotomous variable with a positive (=responder) or negative (=non-reponder) outcome.

The ACR Criteria measures improvement in tender and swollen joint counts in improvement in at least three or the following parameters:

- 1. Patient assessment
- 2. Physician assessment
- 3. Pain scale
- 4. Disability/functional questionnaire
- 5. Acute phase reactant (ESR or CRP)

ACR 20 has a positive outcome if 20% improvement in tender and swollen joint counts were achieved as well as 20% improvement in at least three of the other five criteria.

ACR 50 has a positive outcome if 50% improvement in tender and swollen joint counts were achieved as well as 50% improvement in at least three of the other five criteria.

ACR 70 has a positive outcome if 70% improvement in tender and swollen joint counts were achieved as well as 70% improvement in at least three of the other five criteria.

Confidential Page 84 of 89

Appendix 6 HAQ-DI© Questionnaire

HEALTH ASSESSMENT QUESTIONNAIRE (HAQ-DI)©

Name:		Date:			
Please place an "x" in the box which best	describes your at	oilities OVER T	HE PAST WEEK:	:	
	WITHOUT ANY DIFFICULTY	WITH SOME DIFFICULTY	WITH MUCH DIFFICULTY	UNABLE TO DO	
DRESSING & GROOMING					
Are you able to:					
Dress yourself, including shoelaces and but	tons?				
Shampoo your hair?					
ARISING			_		
Are you able to:					
Stand up from a straight chair?					
Get in and out of bed?					
EATING					
Are you able to:					
Cut your own meat?					
Lift a full cup or glass to your mouth?					
Open a new milk carton?					
WALKING					
Are you able to:	_				
Walk outdoors on flat ground?					
Climb up five steps?					
Please check any AIDS OR DEVICES that	you usually use fo	or any of the ab	ove activities:		
Devices used for Dressing	Built up or special	utensils [Crutches		
(button hook, zipper pull, etc.)	Cane	[Wheelchair		
Special or built up chair	Walker				
Please check any categories for which you	u usually need HE	LP FROM AND	THER PERSON:		
Dressing and grooming	Arising	Eating	☐ Walk	ring	

Confidential Page 85 of 89

Please place an "x" in the box which best describes your abilities OVER THE PAST WEEK:

	WITHOUT ANY DIFFICULTY	WITH SOME DIFFICULTY	WITH MUCH DIFFICULTY	UNABLE TO DO			
HYGIENE							
Are you able to:							
Wash and dry your body?							
Take a tub bath?							
Get on and off the toilet?							
REACH			_				
Are you able to:							
Reach and get down a 5 pound object (such as a bag of sugar) from above your head?							
Bend down to pick up clothing from the floor?							
GRIP							
Are you able to:							
Open car doors?							
Open previously opened jars?							
Turn faucets on and off?							
ACTIVITIES							
Are you able to:							
Run errands and shop?							
Get in and out of a car?							
Do chores such as vacuuming or yard work?							
Please check any AIDS OR DEVICES that you	usually use fo	or any of the ab	ove activities:				
Raised toilet seat Bathtub bar		Long-han	dled appliances f	for reach			
Bathtub seat Long-handled apprint bathroom	oliances	Jar opener (for jars previously opened)					
Please check any categories for which you usually need HELP FROM ANOTHER PERSON:							
Hygiene Reach Gripping and opening things Errands and chores							

Your ACTIVITIES: To what extent are you able to carry out your everyday physical activities such as walking, climbing stairs, carrying groceries, or moving a chair?									
	COMPLETELY	MOSTLY	MODERATELY	A LITTLE	NOT AT ALL				
Your PAIN: How much pain have you had IN THE PAST WEEK? On a scale of 0 to 100 (where zero represents "no pain" and 100 represents "severe pain"), please record the number below.									
Your HEALTH: Please rate how well you are doing on a scale of 0 to 100 (0 represents "very well" and 100 represents "very poor" health), please record the number below.									

 $Courtesy\ of\ https://integrationacademy.ahrq.gov/center/default/files/-DI_0.pdf$

- Added description of analysis of qualitative assessments to section 4.2.3
- Added description of analysis of the additive effect of either quantitative or qualitative assessment of Tc 99m tilmanocept imaging to section 4.2.3
- Modified description of concordance of improvement classification of each algorithm with clinical improvement criteria to indicate that p-values for sensitivity and specificity will be included
- Added tables for concordance of qualitative assessment of Tc 99m tilmanocept imaging with clinical improvement criteria
- Added tables for concordance of qualitative plus quantitative assessment of Tc 99m tilmanocept imaging with clinical improvement criteria
- Added tables for summary of generalized linear mixed model to asses the additive effect of either quantitative or qualitative assessment of Tc 99m tilmanocept imaging on patient response status
- Added p-values for all clinical assessments in addition to those for ACR50 to tables 15-22
- Added data listing for qualitative imaging assessments
- Added data listing for qualitative plus quantitative assessments which differ from original quantitative assessment
- Updated TLF table of contents to remove redundant tables
- Added new tables and listings to TLF table of contents
- Renumbered TLFs to include new additions

Version 1.0 to 2.0

- Changed intent-to-diagnose population in section 2.2 to include all subjects who were injected with Tc 99m tilmanocept at visit 2 and received planar imaging of the hands at visit 2, regardless of if they received any other assessments.
- Changed wording in section 1.3 to specify that at least the same two of three readers must reject both null hypotheses for the two co-primary endpoints to be achieved.
- Added detail in section 2.3 regarding imputation strategies, and proposed secondary imputation strategy for some missing data scenarios if primary imputation strategy does not work.
- Added detail in section 4.1.1.1 regarding the possibility for a patient's TUV prediction from bucketing vs. non-bucketing to differ, and how these findings will be summarized.
- Added tables 27-28 to summarize the number of patients who TUV predictions from bucketing vs. non-bucketing differ.
- Added data listing 28 to provide detail on patients who TUV predictions from bucketing vs. non-bucketing differ.

Table of Contents

APPROVAL PAGE
REVISION HISTORY
LIST OF ABBREVIATIONS AND DEFINITIONS OF TERMS
INTRODUCTION

6.1 Patient Completion
6.1 Patient Completion276.2 Physical Exam276.3 Study Drug Administration28
6.1 Patient Completion276.2 Physical Exam276.3 Study Drug Administration286.4 RA Evaluation and Screening Physical Exam28
6.1 Patient Completion276.2 Physical Exam276.3 Study Drug Administration286.4 RA Evaluation and Screening Physical Exam286.5 Concomitant Medications28
6.1 Patient Completion276.2 Physical Exam276.3 Study Drug Administration286.4 RA Evaluation and Screening Physical Exam286.5 Concomitant Medications287.0 LIST OF ANALYSIS TABLES, FIGURES AND LISTINGS29
6.1 Patient Completion276.2 Physical Exam276.3 Study Drug Administration286.4 RA Evaluation and Screening Physical Exam286.5 Concomitant Medications287.0 LIST OF ANALYSIS TABLES, FIGURES AND LISTINGS298.0 REFERENCES33
6.1 Patient Completion.276.2 Physical Exam276.3 Study Drug Administration.286.4 RA Evaluation and Screening Physical Exam286.5 Concomitant Medications.287.0 LIST OF ANALYSIS TABLES, FIGURES AND LISTINGS298.0 REFERENCES.33APPENDIX A – TABLES, FIGURES AND LISTING SPECIFICATIONS34

Term	Definition		
Δ	Greek letter delta, used to represent the change in a particular		
	variable		
μg	microgram		
ACPA	anti-citrullinated protein/peptide antibody		
ACR/EULAR	American College of Rheumatology/ Furopean League		
	Against Rheumatism		
AE	adverse event		
Anti-TNF-α	Anti-Tumor Necrosis Factor α biological Disease Modifying		
bDMARD	Anti-Rheumatic Drug		
CDAI	Clinical Disease Activity Index		
CFB	change from baseline		
CI	confidence interval		
CRF	case report form		
СТ	X-ray computed tomography		
DAS28	Disease activity score used with the ACR/EULAR 2010 RA		
	guidelines		
ECG	electrocardiogram		
FDA	Food and Drug Administration		
HAQ-DI	Health Assessment Questionnaire Disability Index		
HC(s)	healthy control(s)		
ICH	International Conference on Harmonization		
ITD	intent-to-diagnose		
IV	intravenous		
mCi	milliCurie (37x10 ⁶ becquerels; 37megabecquerels)		
MCP	metacarpophalangeal		
MedDRA	Medical Dictionary for Regulatory Activities		
MI	macrophage-involved contribution		
NPV	Negative Predictive Value		
OA	Overall Accuracy		
PIP	proximal interphalangeal		
PP	per protocol		
PPV	Positive Predictive Value		
PR	the time from the onset of the P wave to the start of the QRS		
	complex		
QRS	time from the start of the Q wave to the end of the S wave,		
	representing ventricular depolarization		
QT	time from the start of the Q wave to the end of the T wave		
QTcF	QT interval with Fridericia's correction formula		
RA	rheumatoid arthritis		
ROI	region of interest		
SAE	serious adverse event		

List of Abbreviations and Definitions of Terms

Term	Definition
SAP	statistical analysis plan
SJC	swollen joint count
SOC	system organ class
SPECT	single photon emission computed tomography
Tc 99m	technetium-99m metastable isotope; γ -emitting (half-life 6.02
	h)
TEAE	treatment-emergent adverse event
TESAE	treatment-emergent serious adverse event
tilmanocept	DTPA Mannosyl Dextran (the US Adopted Name for the drug
	substance of Lymphoseek)
TJC	tender joint count
TUV	Tilmanocept uptake value
US	United States
WPI	Widespread Pain Index

INTRODUCTION

Description

This statistical analysis plan (SAP) is consistent with Amendment #3 of the study protocol (dated 29 September 2023) and includes details of efficacy and safety summaries for use in support of the planned trial, as outlined in ICH E3 (Structure and Content of Clinical Study Reports) and ICH E9 (Statistical Principles for Clinical Trials). Considerations were also given to the FDA Guidance for industry on Developing Medical Imaging Drug and Biological Products Part 3: Design, Analysis, and Interpretation of Clinical Studies (June 2004), FDA Guidance for Industry on Clinical Trial Imaging Endpoint Process Standards (April 2018) and Statistical Guidance on Reporting Results from Studies Evaluating Diagnostic Tests - Guidance for Industry and FDA Staff (March 2007). The study design and analysis plans align with recommendations received from the US FDA at the End of Phase 2 meeting on 01 September 2021 (IND 132943).

1.0 Synopsis of Study Design/Procedures

This is a prospective, multicenter, open-label study designed to evaluate the early predictive capacity of quantitative Tc 99m tilmanocept planar imaging for downstream clinical response(s) in individuals with moderate to severe rheumatoid arthritis (RA) who are candidates for change in anti-TNF α therapy. Temporal changes (from baseline to 5-weeks) in quantitative imaging will be correlated with longitudinal changes (from baseline to 12 weeks and baseline to 24 weeks) in RA clinical assessments, with the intent of evaluating the clinical utility of Tc 99m tilmanocept for the expedited evaluation of antirheumatic treatment efficacy when compared with longitudinal assessments in clinical practice.

The study objectives are as follows:

Primary:

- To demonstrate that global tilmanocept uptake values (TUV_{global}) obtained before initiation of anti-TNFa therapy (TUV_{global[b]}) and at 5 weeks ± 1 week following change in therapy (TUV_{global[5w]}) has a specificity of greater than 80% to correctly specify a clinical nonresponse to therapy at 24 weeks.
- To demonstrate that TUV_{global} obtained before initiation of anti-TNFα therapy and at 5 weeks ± 1 week following change in therapy has a sensitivity of greater than 65% to correctly classify a positive clinical response to therapy at 24 weeks.

Key Secondary

 To evaluate the negative predictive value (NPV) of TUV_{global} obtained before initiation of anti-TNFα therapy (TUV_{global[b]}) relative to a clinical non-response to therapy at 24 weeks.

Secondary

- To evaluate the sensitivity and specificity of TUV_{global} obtained before initiation of anti-TNF α therapy and at 5 weeks ± 1 week following change in therapy relative to a positive clinical response or a non-response to therapy at 12 weeks.
- To evaluate the NPV of TUV_{global[b]} relative to a clinical non-response to therapy at 12 weeks.
- To evaluate the positive predictive value (PPV), NPV, and overall accuracy (OA) of TUV_{global} obtained before initiation of anti-TNF α therapy and at 5 weeks ± 1 week (Δ TUVglobal_[5w]) following change in therapy relative to a positive clinical response or a non-response to therapy at 12 and/or 24 weeks.
- To evaluate the qualitative assessment of Tc 99m tilmanocept imaging to predict clinical response or non-response following a change in anti-TNFα therapy.
- To evaluate the additive effect of either quantitative or qualitative assessment of Tc 99m tilmanocept imaging to the other at baseline and change from baseline to 5 weeks \pm 1 week to predict clinical response or non-response following a change in anti-TNF α therapy.
- To evaluate the correlation of changes in TUV_{global} obtained before initiation of anti-TNFα therapy and at 5 weeks ± 1 week following a change in therapy with changes in composite clinical assessments and their constituent parameters at 12 and/or 24 weeks.
- To evaluate the correlation of changes in TUV_{global} obtained before initiation of anti-TNF α therapy and at 5 weeks ± 1 week following a change in therapy with changes in clinical assessments at 12 and/or 24 weeks for specific anti-TNF α bDMARD agents.
- To evaluate the ability of changes in TUV_{global} obtained before initiation of anti-TNF α therapy and at 12 weeks ± 1 week following change in therapy to accurately predict a clinical response or non-response at 24 weeks.
- To evaluate the correlation of changes with TUV_{global} and changes in clinical RA assessments as a means to monitor therapy.
- To evaluate sensitivity and specificity in patient subgroups.

• To evaluate the safety of IV-administered tilmanocept radiolabeled with Tc 99m.

The statistical endpoints that address these objectives are defined in Section 4 (efficacy) and Section 5 (safety). Refer to Section 2.2.1 for subgroup definitions and considerations.

1.1 Design and Treatment

This is a prospective, open-label, multicenter study designed to evaluate the early predictive capacity of quantitative Tc 99m tilmanocept planar imaging for downstream clinical response(s) in individuals with moderate to severe RA who are candidates for change in anti-TNF α therapy.

All patients will receive an IV dose of 150 mcg tilmanocept radiolabeled with 10 mCi of Tc 99m prior to imaging.

1.2 Study Procedures

Prior to the initiation of a new anti-TNF α therapy, patients will undergo baseline rheumatological evaluations of ACR/EULAR 2010, Clinical Disease Activity Index (CDAI), DAS28, and Health Assessment Questionnaire Disability Index (HAQ-DI) for the characterization of disease activity. After these evaluations, patients will receive an IV dose of 150 mcg tilmanocept radiolabeled with 10 mCi of Tc 99m and undergo baseline planar imaging of the bilateral hands and wrists. Upon completion of baseline imaging procedures, patients will commence a new anti-TNF α bDMARD treatment regimen and return to the clinic 5 +/- 1 weeks, 12 +/- 1 weeks, and 24 +/- 1 weeks later for a series of rheumatological evaluations (including CDAI, DAS28, ACR Response Criteria, and HAQ-DI), drug administration, and bilateral hand/wrist imaging.

Images will undergo centralized quantification for the derivation of joint-specific and global TUV. At the joint level, TUV is defined as the intrapatient ratio of the average pixel intensity of a joint to the average pixel intensity of the reference region. TUV_{global} is a per patient summary of TUV_{joint} values greater than the normative database representing RA-specific inflammation.

All images will be read by three nuclear medicine specialists trained in the reading of these images. Each reader will work independently of the other readers. Each reader will provide both a qualitative read and map regions of interest for calculation of TUV.

Temporal differences in TUV_{global} from baseline to 5 +/- 1 weeks of therapy (Δ TUV_{global[5w]}) will be compared with longitudinal clinical outcomes at 12 +/- 1

and 24 +/- 1 weeks of therapy defined by changes in CDAI (Δ CDAI_[12/24w]), changes in ACR Response Criteria (Δ ACR_[12/24w]), and changes in DAS28 (Δ DAS28_[12/24w]) to evaluate the efficacy of TUV_{global} for the accelerated prediction of clinical response to antirheumatic drugs.

Refer to the clinical study protocol for further details on the study procedures and for the schedule of events table.

1.3 Sample Size

NAV3-33 is sized with respect to achieving specified goals in the co-primary endpoints of sensitivity and specificity of $\Delta TUV_{global[5w]}$ with bucketing. Sensitivity and specificity require knowledge of the patient's clinical status at Week 24, and so hypothesis testing will be performed after classification. The value of $\Delta TUV_{global[5w]}$ necessary to predict response vs. non-response and the value of $TUV_{global[5w]}$ necessary to predict response vs. non-response and the value of TUV_{global[b]} at baseline necessary to predict non-response will be determined in advance. The classification procedure occurs in two stages, following the baseline image acquisition and (possibly) following the 5 week image acquisition and calculation of $\Delta TUV_{global[5w]}$. After the baseline imaging, patients whose TUV_{global[5w]} is available, patients whose TUV_{global[b]} is ≥ 5 and D% is $\leq -10\%$ are predicted to be responders. All other patients are predicted to be non-responders. The Week 24 ACR50 will be used as the primary determination of clinical response for the reference standard

The hypotheses for the co-primary endpoints to be tested are:

$$H_{O1}: \pi_{Sp} \le 0.8$$

 $H_{A1}: \pi_{Sp} > 0.8;$

And

 $H_{02}: \pi_{Se} \le 0.65$ $H_{A2}: \pi_{Se} > 0.65.$

In the above π_{Sp} represents the true specificity of the classification procedure and π_{Se} represents the true sensitivity of the classification procedure when used to predict the outcome of the anti-TNF α bDMARD inhibitor therapy at 24 weeks. An overall two-tailed Type I error rate of 0.05 (one-tailed 0.025) was used without adjusting for multiple endpoints, as both co-primary endpoints must be achieved in order to have a successful study. If the actual specificity is 0.92 and the actual sensitivity is 0.8, and if an exact binomial test is used to test the above hypotheses, a total of 98 clinical non-responders and 100 clinical responders are needed for 90% power of the individual tests. That is, a minimum of 198 total patients is needed. This applies to a single reader.

To evaluate the power characteristics of this process with 3 correlated readers where at least the same two of the three readers must reject both null hypotheses above, a simulation study was performed. Correlated binomial random variables were generated using a copula. The hypotheses were tested for each simulated reader using an exact binomial test, and the number of iterations where at least the same two of the three readers rejected both hypotheses was counted. Under the conditions above this procedure has power 0.93 when $\rho = 0.7$ and 0.89 when $\rho = 0.9$.

In Arm 3 of the NAV3-31 study a ratio of 5 non-responders to 1 responder was observed. If this ratio is maintained in NAV3-33 for the $\Delta TUV_{global[5w]}$ with bucketing predictions, a total of 600 patients is needed to achieve the desired power. That is, a total of 500 clinical non-responder patients is expected to be enrolled before reaching the required 100 clinical responders.

Taking into account a 10% dropout rate, the anticipated total sample size for the study is approximately 672 patients (560 clinical non-responders and 112 clinical responders). That is:

- Clinical Non-Responders: 90% completion rate relative to 560 enrolled patients will result in 500 completed patients
- Clinical Responders: 90% completion rate relative to 112 enrolled patients will result in 100 completed patients

Because there is uncertainty about how responding and non-responding patients will enroll, enrollment may continue until at least 560 clinical non-responders and 112 clinical responders are participating in the study. The cumulative enrollment of clinical non-responders and responders will be tracked throughout the study in order to stop enrollment once the required number has been reached for each clinical category. This tracking of clinical response and non-response status will be performed by individuals without knowledge of the TUV data. At the Sponsor's discretion, the week 12 clinical response outcomes may be used to help track enrollment.

If the two co-primary endpoints are achieved (i.e., both null hypotheses are rejected for at least the same 2 out of 3 readers), then the following hypotheses will be tested at one-tailed 0.025 for the key secondary endpoint of NPV of TUV_{global[b]} with respect to ACR50 at week 24:

$$H_{03}: \pi_{\text{NPV}} \le 0.7$$

 $H_{A3}: \pi_{\text{NPV}} > 0.7;$

If the actual NPV is 0.85, and if an exact binomial test is used to test the above hypotheses, a total of 89 predicted non-responders using $TUV_{global[b]}$ are needed for 90% power and a total of 71 non-responders using $TUV_{global[b]}$ are needed for 80% power. Enrollment of predicted non-responders at baseline will be tracked in order to ensure enough subjects are enrolled to achieve at least 80% power for this endpoint.

All enrollment tracking will be done in aggregate by individuals without knowledge of the subject-level data. Enrollment tracking will include the total number of predicted non-responders at baseline, the total number of clinical responders at or beyond week 12, and the total number of clinical non-responders at or beyond week 12.

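### The stated overall power (0.93 at ρ = 0.7, 0.89 at ρ = 0.9) does not follow from 98 non-responders and 100 responders; it is about 0.86–0.88 and 0.84–0.86

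*SAP*

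**What the plan says.** SAP section 1.3 sets specificity above 0.80 and sensitivity above 0.65 as the co-primary goals. On the error rate it says: "An overall two-tailed Type I error rate of 0.05 (one-tailed 0.025) was used without adjusting for multiple endpoints". The design alternative is "If the actual specificity is 0.92 and the actual sensitivity is 0.8, and if an exact binomial test is used", which leads to "a total of 98 clinical non-responders and 100 clinical responders are needed for 90% power of the individual tests". The SAP adds of the resulting 198: "This applies to a single reader".

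The next paragraph turns to the real success criterion: "at least the same two of the three readers must reject both null hypotheses above, a simulation study was performed". Its result is reported as: "Under the conditions above this procedure has power 0.93 when" ρ = 0.7, and 0.89 when ρ = 0.9. The reads are said to come from a copula. The copula family, the level at which ρ applies (patient reads or reader counts), the patients per category and the number of runs are not given.

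Only after that sentence does the text bring in the 5:1 ratio, the 500 expected non-responders, and the 560 + 112 = 672 enrolled. Protocol section 9.4 and the Statistical Methods part of the protocol synopsis carry the same statement in the same order.

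**The concern.** The conditions that precede the power sentence are 98 and 100 patients, each test powered at about 90%. A reader who must pass two tests with roughly 0.91 power on separate patient groups passes both about 83% of the time. Asking for two of three such readers raises that figure, but the gain is largest when readers are independent and vanishes as they come to agree. A claim of 0.93 at a correlation as high as 0.7 therefore looked too high on its face.

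This is the only power figure given for the criterion that decides the trial. The protocol allows 198 to 672 evaluable subjects (synopsis and section 8.1.1). SAP section 1.3 says enrollment may continue to 560 and 112, where protocol section 9.4 says it will. A reader could conclude that a trial stopped near 198 has about 0.9 power for success.

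**Working it through.** **Inputs (SAP section 1.3).** Null and true specificity 0.80 and 0.92; null and true sensitivity 0.65 and 0.80; exact binomial tests at one-sided 0.025; 98 non-responders and 100 responders; success if at least the same two of three readers reject both nulls.

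**Step 1: reproduce the single tests.** Take the smallest count whose upper tail under the null is at most 0.025.

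- Specificity: P(X ≥ 86 | 98, 0.80) = 0.0312 and P(X ≥ 87 | 98, 0.80) = 0.0158, so reject at 87 or more. Power = P(X ≥ 87 | 98, 0.92) = 0.908.
- Sensitivity: P(X ≥ 74 | 100, 0.65) = 0.0351 and P(X ≥ 75 | 100, 0.65) = 0.0211, so reject at 75 or more. Power = P(X ≥ 75 | 100, 0.80) = 0.913.

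The 90% for each individual test is confirmed.

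**Step 2: one reader, both tests.** Specificity and sensitivity have different denominators in the 2 × 2 table of SAP section 4.2.1 (T4 and T3), so they rest on different patients. Joint power p = 0.9082 × 0.9125 = 0.8288.

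**Step 3: limits for two of three readers.**

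- Independent readers: 3p² − 2p³ = 3(0.6869) − 2(0.5693) = 0.922.
- Readers in perfect agreement: p = 0.829.

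**Step 4: correlated readers.** The SAP does not define the copula, so I simulated two natural versions. One places an exchangeable Gaussian copula on the readers' counts, separately for each endpoint. The other places it on the patient-level reads. Monte Carlo standard errors are at most 0.002.

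| Patients (non-responders/responders) | Model | ρ = 0.7 | ρ = 0.9 |
|---|---|---|---|
| Stated in SAP | not given | 0.93 | 0.89 |
| 98/100 | counts | 0.857 | 0.838 |
| 98/100 | patient reads | 0.88 | 0.86 |
| 500/100 | counts | 0.931 | 0.919 |
| 500/100 | patient reads | 0.945 | 0.930 |

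If ρ is instead the Pearson correlation of the binary reads, 98/100 gives 0.857 and 0.832. Kendall and Spearman readings of ρ, and Gumbel copulas, gave 0.836–0.855 at ρ = 0.7 and 0.827–0.838 at ρ = 0.9.

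**Step 5: could another sample size explain the pair?** At 500/100 the specificity test has power close to 1, so a single reader's joint power is the sensitivity power, 0.913. Perfectly agreeing readers would therefore give 0.913. The stated 0.89 lies below that, so 500/100 cannot produce it. The 0.93 is too high for 98/100, and the 0.89 is too low for 500/100.

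**Step 6: departures that come close.** Two departures land within 2 points of both figures. One-sided 0.05 with a copula on counts gives 0.922 and 0.906. A rule that any one reader suffices gives 0.945 and 0.902. Each contradicts the text. Either might point to the slip, but the documents do not show which.

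**The case against.** Four points can be made for the plan.

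- **The excess over independent readers is small.** It is 0.93 against 0.922, or 0.008. If the simulation used, say, 1,000 runs (an assumption), its standard error would be √(0.93 × 0.07 / 1000) = 0.008. This stands: the comparison would not be decisive alone. The weight rests on the gaps at the stated correlations, 5–7 points at ρ = 0.7 and 3–5 points at ρ = 0.9.
- **Each figure can be reached separately under some copula.** One copula across all six counts gives 0.878 and 0.887, which matches 0.89. Using the same random draw for both endpoints gives 0.928 and 0.914, which matches 0.93. Neither gives the pair, and both tie together two endpoints measured on different patients.
- **The working plan is larger than 198.** At 500/100 completers, power for the success rule is above 0.90 at both correlations. This stands and limits the consequence. The added risk applies only if the trial ends near its 198 floor, which the documents permit.
- **The text already says that 90% belongs to the individual tests and that 198 is for one reader.** That is true, but the next paragraph attaches 0.93 and 0.89 to those same conditions, which undoes the caution.

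**Conclusion.** The power statement is wrong as written. At 98/100, one-sided 0.025 and the stated rule, power is about 0.86–0.88 at ρ = 0.7 (stated 0.93) and 0.84–0.86 at ρ = 0.9 (stated 0.89). The chance of missing the co-primary goal is 12–14% rather than 7% at ρ = 0.7, and 14–16% rather than 11% at ρ = 0.9.

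These ranges assume Gaussian dependence between readers and independence of sensitivity and specificity within a reader. The other copulas and meanings of ρ in step 4 give somewhat lower values. The single-reader figure of 0.829 and the independent-reader value of 0.922 need no copula, only the within-reader independence that disjoint patients support.

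The hypotheses, the error rate, the analysis and the planned total are unaffected.

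**What to change.** In SAP section 1.3, protocol section 9.4 and the protocol synopsis, replace the power sentence with results from a rerun. State the patients per category, the one-sided level, the copula family, whether ρ applies to patient reads or reader counts, and the number of runs.

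Report two cases separately:

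- **98/100:** the single-reader joint power (0.83) and the two-of-three power, which I expect at about 0.86–0.88 (ρ = 0.7) and 0.84–0.86 (ρ = 0.9).
- **500/100:** the expected completers, at about 0.93–0.95 and 0.92–0.93.

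The sponsor's final values will depend on the copula it declares. Next to the new figures, repeat that 90% applies to each test alone. Check the existing code for the level used and for how the two-of-three rule is counted.

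The cost is a short simulation and edits in three places, with no extra patients. The 198 minimum will look less favourable.
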